5.2 Secondary Efficacy Endpoints

The following secondary efficacy endpoints, as derived from the e-diary, are the change from baseline to the end of the 12-week treatment period in children (5 to <12 years of age) in:

- Mean volume voided per 24 hours
- Maximum volume voided
- Mean number of daytime incontinence episodes per 24 hours
- Mean number of nighttime incontinence episodes per 24 hours
- Mean number of daytime micturitions per 24 hours
- Number of dry (incontinence free) days per 7 days

For all above secondary efficacy endpoints the value calculated from the e-diary period 7 days before visit 3/week 0/baseline will be regarded as the baseline value.

5.2.1 Mean Volume Voided per 24 hours

Mean volume voided is derived from "Pee Volume" of the 2-day Weekend Episodic Diary.

For each subject, the mean volume voided per day will be calculated as the sum of the volumes voided on that (valid diary) day divided by the number of times a volume was recorded on that day in the 2-day Weekend Episodic Diary.

The mean volume voided at Visit x (x=4, 5, 6, and 7) will be calculated as the mean value of the mean volumes voided on each of the two days

If volumes are recorded on 1 single (valid) day of the 2-day Weekend Episodic Diary, then the mean volume will be the sum of all available volumes of that day divided by the number of times a volume was recorded.

If no volumes are recorded on either (valid) measuring day, then the mean volume will be missing.

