5 EFFICACY AND SAFETY ENDPOINTS

Data for the efficacy endpoints will be recorded on an e-diary. This e-diary consists of a:

- 5-day Weekday Diary (bladder diary, Monday Friday), which is used for a 5-day period to record micturition frequency and incontinence episodes, and
- 2-day Weekend Episodic Diary (Saturday and Sunday), which is used to record micturition frequency, incontinence episodes, (pee) volume measurements, and worst leakage severity.

A valid diary day for:

• "Volumes"

In the 2-day Weekend Episodic Diary, is any e-diary day for which at least one "Pee Volume" greater than 0 mL is recorded with complete date and time.

- "Micturitions"
- In 2-day Weekend Episodic Diary, is any diary day for which at least once "Pee Volume" greater than 0 is recorded.
- In 5-day Week Diary, is any diary day for which the response to the question "Number of times using the toilet during the day/night" is not missing.
 - "Incontinence episodes"
- In 2-day Weekend Episodic Diary, is any diary day for which at least:
 - One micturition ("Pee Volume" >0) and
 - One "Leakage" or "Pee in toilet and Leakage" are recorded.
- In 5-day Week Diary, is any diary day for which:
 - The response to the question "How was your day/night" is not missing.

A valid diary for an analysis visit is a diary with at least 4 valid diary days within that analysis visit window. If for more than 7 days the diary is filled in prior to a visit, only the last 7 days prior to that visit will be used for calculation of the efficacy endpoints.

The number of valid diary days: Count of the valid diary days during the 7-day diary period. Days of visits to the clinic will not be counted as valid diary days.

In the event that in the 2-day Weekend Episodic Diary there are two entries with the same collection date and time but with different times of entry on the device, the last entry (time) will be used for analysis.

For several of the secondary efficacy endpoints, diary data will be classified as either "daytime" or "nighttime", where "daytime" is considered to mean "between waking up in the morning and going to sleep later the same day or next day" and "nighttime" means "between going to sleep on a day and waking up on the same or next day".

Whether an entry into the 5-day Week Diary is done during daytime or nighttime is captured on this diary.

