5.3.4 Mean Number of Micturitions per 24 hours, Adjusted for Fluid Intake

For this endpoint the voided volumes will be taken as surrogate for the fluid intake.

In Sender Herschorn *et al.*, (2017) page 56 Materials and Methods, the following subdivision is presented of the number of micturitions at a visit, say visit x.

Number of Micturitions at Visit x (x = 4, 5, 6, and 7) =

Total Volume Voided (Visit x) / Mean Volume Voided (Visit x) =

[Total Volume Voided (Baseline) + Δ Total Volume Voided]/Mean Volume Voided (Visit x) =

Total Volume Voided(Baseline) / Mean Volume Voided(Visit x) +

 Δ Total Volume Voided / Mean Volume Voided(Visit x),

where Δ is the difference in total volume voided between Visit x and Baseline [=Total Volume Voided (Visit x) – Total Volume Voided (Baseline)].

This can be viewed as a partition of Number of Micturitions at Visit x into 2 parts as follows:

- Total Volume Voided (Baseline) / Mean Volume Voided (Visit x) is the number of micturitions per 24 hours that would be required at Visit x to void the total daily volume, if this total volume remains unchanged from baseline, that is, if treatment did not affect subjects' fluid intake.
- Δ Total Volume Voided / Mean Volume Voided(Visit x) is the additional number of micturitions per 24 hours (vs baseline) required to void the extra fluid intake.

For each subject, the Mean Change in Number of Micturitions per 24 hours at Visit x (x=4, 5, 6, and 7), adjusted for fluid intake will be calculated as:

Total Volume Voided at Visit x -Total Volume Voided at BaselineMean Volume Voided per Micturition at Visit x

Example:

A subject voided the following volumes:

- At baseline, Saturday: 200 ml, 200 ml, 200 ml, 200 ml and 200 ml, and Sunday: 200 ml, 200 ml, 200 ml and 200 ml
- At visit x, Saturday: 250 ml, 250 ml, 250 ml and 250 ml, and Sunday: 250 ml, 250 ml and 250 ml

This results in:

Total Volumes Voided per 24 hours at baseline and at visit x are 900 ml and 875 ml, respectively. Mean Volume Voided per 24 hours at visit x is 250 ml,

Total Volume Voided (baseline) / Mean Volume Voided (visit x) = 900 ml / 250 ml = 3.6, which means that 3.6 micturitions per 24 hours would be required at visit x to void the same total volume as voided at baseline (3.6 x 250 = 900 ml). This is the expected mean number of micturitions per 24 hours at visit x.

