6.4.2 Analysis of Secondary Efficacy Endpoints

Descriptive statistics (n, mean, SD, minimum, median, maximum) and the same primary efficacy analysis (ANCOVA) as for the primary endpoint will be applied to change from baseline at the end of the 12-week treatment period in children (5 to <12 years of age) for:

- Mean volume voided per 24 hours
- Maximum volume voided
- Mean number of daytime incontinence episodes per 24 hours
- Mean number of daytime micturitions per 24 hours

Change from baseline in the number of dry (incontinence free) days per 7 days at the end of the 12-week treatment period will be analyzed with a negative binomial regression model including treatment group, sex, geographical region as factors and the log baseline rate of number of dry days (e.g., the log of the ratio of dry days and number of diary days at baseline) as covariate.

Data of these secondary efficacy endpoints will be analyzed both without imputation and with imputation using the LOCF method, for the FAS.

The same analysis detailed in Section 6.4.1.3 will be performed for all the secondary efficacy endpoints on the FAS as sensitivity analysis.

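### The secondary endpoint named as volume voided per 24 hours is derived in SAP 5.2.1 as mean volume per recorded void, so the analysis does not deliver the quantity it names

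*SAP*

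**What the plan says.** **Name.** The endpoint is called "Mean volume voided per 24 hours" in SAP 6.4.2. The same label appears in the protocol synopsis, protocol Table 5 and protocol 9.4.2, and in SAP Table 1, SAP 5.2 and the heading of SAP 5.2.1. Adolescents have an exploratory endpoint of the same name (protocol 9.4.3; SAP 5.3 item 8, 5.3.6 and 6.4.3), and SAP 5.3.6 simply refers back to 5.2.1.

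**Derivation.** The protocol gives none. SAP 5.2.1 takes, for each weekend diary day, "the sum of the volumes voided on that (valid diary) day divided by the number of times a volume was recorded on that day". The visit value "will be calculated as the mean value of the mean volumes voided on each of the two days". If only one valid day has volumes, that day is used alone. The value is missing only when neither day has a volume.

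**Use.** SAP 6.4.2 applies the primary ANCOVA to the change from baseline in this variable, with and without LOCF, and repeats the sensitivity analyses of SAP 6.4.1.3 on it. Protocol 9.1 and SAP 3 say that efficacy in children rests on the primary and secondary endpoints together.

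**Other wording for the same number.** SAP 5.3.4 works through one subject and reports "Total Volumes Voided per 24 hours at baseline and at visit x are 900 ml and 875 ml, respectively", followed by "Mean Volume Voided per 24 hours at visit x is 250 ml". The formula in that section calls the same denominator a volume per micturition. SAP Table 1 and 6.4.3 also use the per-micturition name for the endpoint expressed as a percentage of expected bladder capacity.

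**The concern.** Dividing a day's total by the number of recorded voids gives an average void. Averaging that over two days leaves the unit as mL per void; it does not become a daily volume. The name promises one quantity and the derivation produces another.

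The two answer different questions. Volume per void reflects how much the bladder holds before the child voids. Volume per 24 hours reflects urine output and hence intake: SAP 5.3.4 itself uses voided volume as a stand-in for fluid intake. Protocol 7.6 asks that intake on volume-measuring days be kept as constant as possible, so a true 24-hour volume is held steady by design while the average void remains free to change. A treatment effect on the average void, reported under a per-24-hours name, could be read as children drinking and passing more.

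This endpoint is formally tested and is part of the stated basis for judging efficacy in children. Someone with only the protocol, or only a results table carrying the endpoint's name, could not tell which quantity was analysed.

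**Working it through.** **Inputs** (SAP 5.3.4, illustrative subject):
- Baseline: five voids on Saturday and four on Sunday, each of 200 mL.
- Visit x: four voids on Saturday and three on Sunday, each of 250 mL.

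**Formulas**
- 24-hour volume T = mean over the two days of each day's summed volume.
- SAP 5.2.1 value V = mean over the two days of (day's summed volume / number of volumes recorded that day).
- Voids per 24 hours K = mean over the two days of the number of voids.

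**Reproducing the SAP's own figures**
- T at baseline = (5 × 200 + 4 × 200)/2 = (1000 + 800)/2 = 900 mL. SAP: 900.
- T at visit x = (4 × 250 + 3 × 250)/2 = (1000 + 750)/2 = 875 mL. SAP: 875.
- V at visit x = (1000/4 + 750/3)/2 = 250 mL. SAP: 250.
- K = (5 + 4)/2 = 4.5 at baseline and (4 + 3)/2 = 3.5 at visit x. SAP: 4.5 and 3.5.
- T at baseline / V at visit x = 900/250 = 3.6, and (875 - 900)/250 = -0.1. SAP: 3.6 and -0.1.

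All match.

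**The step the SAP does not show**
- V at baseline = (1000/5 + 800/4)/2 = 200 mL.

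| Quantity | Baseline | Visit x | Change |
|---|---|---|---|
| As derived in SAP 5.2.1 (mL per void) | 200 | 250 | +50 |
| As named (mL per 24 hours) | 900 | 875 | -25 |

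**Why the signs differ.** In this example T = K × V (4.5 × 200 = 900; 3.5 × 250 = 875). V is multiplied by 250/200 = 1.25 and K by 3.5/4.5 = 0.778. The product is 0.972, which equals 875/900. A rise in volume per void combined with a larger proportional fall in the number of voids lowers the daily volume. Fewer voids is the benefit the primary endpoint looks for, so this is not a contrived pattern.

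**The case against.** The strongest reply is that SAP 5.2.1 is explicit and reproducible, and that the change log in SAP 7.2 records the derivation as having been corrected in version 3.0. The per-void rule therefore looks intended, only the label lags behind, and under a rename no estimate, interval or p-value changes. That much stands. It does not make the point clerical: the label is the definition that protocol readers have, and the SAP left unchanged would report a test of one quantity under the name of another.

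A second reply is that the example is hypothetical, sits in an exploratory section, and separates a total (875 mL) from a mean (250 mL). It is indeed an illustration, not a forecast. The SAP states 900, 875 and 250 mL; the 200 mL baseline and both changes are arithmetic from its inputs. But SAP 5.3.4 attaches the per-24-hours label to both 875 and 250 mL at the same visit, which is the confusion at issue.

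A third reply is that the table specifications are not among the documents. That is correct, so the heading a results table would carry is inferred from the endpoint's name.

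Two stronger readings are tempting and should be resisted.

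- **Every volume value would be missing.** A reader might infer this from SAP 5, which says "A valid diary for an analysis visit is a diary with at least 4 valid diary days within that analysis visit window", while volumes are recorded on only two weekend days. The documents do not support it. SAP 5 defines a valid volume day separately. SAP 5.2.1 and 5.2.2 accept one valid weekend day and set the value to missing only if neither day has a volume. The four-day minimum is restated for 7-day endpoints such as micturitions (5.1) and dry days (5.2.5), but not for volumes.
- **The per-void derivation is itself an error.** A reader might infer this from the name. The change log points the other way, and the protocol is silent.

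**Conclusion.** The mismatch is real and should be resolved. As written, SAP 5.2.1 delivers mean volume per recorded void under a 24-hour name, for a tested secondary endpoint in children and for its adolescent counterpart. In the SAP's own illustrative subject the two quantities differ in level (250 against 875 mL at visit x) and in direction of change (+50 against -25 mL). How far they would diverge in the trial cannot be computed from the documents.

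The conclusion rests on reading SAP 5.2.1 literally and on the protocol giving no competing derivation; both hold in the supplied protocol version 2.0 and SAP version 3.0. Which quantity was meant is not settled: the change log favours per void, the name favours per 24 hours. The primary endpoint, its analysis and the sample size do not depend on this. Nor is there a missing-data problem for the volume endpoints.

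**What to change.** State which quantity is meant, then take one of two routes.

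1. **Keep the derivation and rename.** Call the endpoint *mean volume voided per micturition* everywhere: protocol synopsis, Table 5, 9.4.2 and 9.4.3; SAP Table 1, 5.2, 5.2.1, 5.3 item 8, 5.3.4, 5.3.6, 6.4.2 and 6.4.3; and the table, listing and figure specifications. A partial rename would leave the same inconsistency elsewhere. The protocol part needs a documented amendment, as protocol Appendix 12.1 requires for changes after approval.
2. **Keep the name and change the derivation.** Define the 24-hour volume as each day's summed volume, averaged over the valid weekend days, and report the per-void mean as a separate variable under its own name. SAP 5.1 counts a micturition whether or not its volume was recorded, so this route should also say how a day with unrecorded volumes is handled; such a day would understate the sum.

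Optionally, add a clause to SAP 5 limiting the four-valid-day rule to the 7-day diary endpoints. This is a clarification only, since SAP 5.2.1 and 5.2.2 already give volumes their own rule.

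The cost is wording plus a protocol amendment for route 1, or one additional derived variable and its tables for route 2. Both use data already collected in the weekend diary.

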5.2.2 Maximum Volume Voided

Maximum volume voided data will be derived from "Pee Volume" of the 2-day Weekend Episodic Diary.

For each subject, the maximum volume voided at Visit x (x=4, 5, 6, and 7) is the largest (non-zero) volume recorded over both of the 2 (valid) measuring days in the diary. If volumes are recorded on 1 single (valid) day of the weekend diary, then the maximum volume voided per day is calculated as the largest of all available (non-zero) voided volumes recorded on that day.

If no volumes are recorded on either (valid) measuring day, then maximum volume voided will be missing.

5.2.3 Mean Number of Daytime Incontinence Episodes per 24 hours

For a week day the number of Incontinence Episodes per 24 hours will be derived from "Number of Leakages During the Day" and "Number of Leakages During the Night" of the 5-day Week Diary. Incontinence episodes on measuring days will be classified as daytime or nighttime episodes as entered in the 5-day Week Diary.

For a weekend day the number of incontinence episodes will be derived from the times a "Leakage" or a "Pee in Toilet and Leakage" was entered into the 2-day Weekend Episodic Diary. Whether an Incontinence Episode was during daytime or nighttime will be based on the time-points the subject went to sleep and woke-up.

For each subject, the mean number of incontinence episodes per day/night (during the day/night) at Visit x (x=4, 5, 6, and 7) will be calculated using all available (non-missing) number of incontinence episodes for the valid diary days in the 5-day Week Diary and in the 2-day Weekend Episodic Diary for daytime in the 7-day period before the visit:

Mean No. of Daytime Incontinence Episodes at Visit x =

Total number of "Daytime Leakage Counts" over the Valid Diary Days prior to Visit x Number of Valid Diary Days

5.2.4 Mean Number of Daytime Micturitions per 24 hours

For a week day the daytime micturitions will be derived from "Number of Times using the Toilet During the Day" was entered into the 5-day Week Diary.

For a weekend day the daytime micturitions will be derived from the number of times a "Pee in Toilet" or a "Pee in Toilet and Leakage" was entered into the 2-day Weekend Episodic Diary between the time the subject woke-up (exclusive) and went to sleep (inclusive). However, the first micturition occurring at or after the time of wake-up it is considered a nighttime micturition, see Section 5.1.

The total number of micturitions per weekend day is equal to the total number of times, in the diary, an amount of pee was recorded during daytime for that day.

For each subject, the mean number of daytime micturitions at Visit x (x=4, 5, 6, and 7) in the week before the visit will be calculated as:

Sum of the Number of Daytime Micturitions (per day) over the Valid Diary Days prior to Visit x Number of Valid Diary Days

5.2.5 Number of Dry (incontinence free) Days per 7 Days at the End of the 12-weeks Treatment Period

For a week day a "Dry (incontinence free) Day" is defined as a day where the response is "Dry" to the question "How was your Day" and to "How was your Night".

Let D_{dry} be the number of valid diary days where the response to both questions was "Dry". Let D_{wet} be the number of valid diary days where the response to one of the two questions or to both questions was "Wet".

For a weekend day a "Dry (incontinence free) Day" is defined as a day where no "Leakage" and no "Pee in toilet and leakage" are reported. A "Wet (incontinence) Day" is defined as a day where a "Leakage" or a "Pee in toilet and leakage" is reported.

If $(D_{dry} + D_{wet}) > 3$, then the number of dry days per 7 days at Visit 7 will be calculated for a subject as:

 $\frac{D_{dry}}{(D_{dry}+D_{wet})} \times 7$, otherwise its value is missing.

5.3 Exploratory Endpoints

The following exploratory endpoints, as derived from data collected in the e-diary, are:

- 1. Percentage of subjects with a reduction in daytime incontinence episodes
- 2. Improvement from baseline in worst incontinence grading
- 3. Mean number of micturitions per 24 hours adjusted for fluid intake
- 4. Mean volume voided peer micturition as a percentage of EBC
- 5. Categorized mean volume voided per micturitions a percentage of EBC
- 6. Mean number of micturitions per 24 hours (adolescents only)
- 7. Mean number of daytime micturitions per 24 hours (adolescents only)
- 8. Mean volume voided per 24 hours (adolescents only)
- 9. Maximum volume voided (adolescents only)
- 10. Mean number of incontinence episodes per 24 hours (adolescents only)
- 11. Number of dry (incontinence-free) days per 7 days (adolescents only)
- 12. Mean number of daytime grade 3 or 4 (PPIUS) urgency episodes per 24 hours (adolescents only)

5.3.1 Percentage of Subjects With a Reduction in Daytime Incontinence Episodes (< 50% reduction [non-responder], 50% [partial responder] and 100% [responder])

Number of daytime incontinence episodes per 24 hours will be derived from:

- "Number of leakages during the day" entered into the 5-day Weekday Diary, and
- number of times "Leakage" or "Pee in toilet and leakage" was entered into the 2-day Weekend Episodic Diary between awake time and sleep time.

For each subject, the percent change from baseline to a Visit x (x=4, 5, 6 and 7) in the number of daytime incontinence episodes will be calculated as follows:

R_x = No. Daytime Incontinence Episodes at Visit x – No. Daytime Incontinence Episodes at Baseline No. Daytime Incontinence Episodes at Baseline

× 100%,

where the number of daytime incontinence episodes at Visit x is equal to the sum of the number of incontinence episodes recorded over the 7-day period prior to Visit x. Same calculation for baseline.

If the number of daytime incontinence episodes at baseline is equal to zero, a constant equal to 0.5 will be added to the baseline number of leakages to allow denominator calculation. If the number of daytime incontinence episodes at baseline and/or at a post-baseline visit is missing then the response category in respect to incontinence will be missing.

Definition of responder:

- Complete responder will be defined as a subject with a 100% improvement from baseline (i.e. $R_x = -100\%$).
- Partial responder will be defined as a subject with a percent improvement from baseline \geq 50% and <100% (i.e. -100% < R_X \leq -50%).
- Non-responder will be defined as a subject with an improvement from baseline <50% or a worsening from baseline (i.e. $R_X > -50\%$).

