5.3.2 Improvement from Baseline in Worst Incontinence Grading

Worst Incontinence Grading is derived from:

- The response to "Worst Leakage during the Day" and "Worst Leakage during the Night" from the 5-day Week Diary, and is equal to the worst outcome from both daytime and nighttime responses during a diary day.
- The responses to "Worst Leakage Severity" every time it is reported in the 2-day Weekend Episodic Diary. The worst response to the questions given during a diary day will be used for analysis.

Possible outcomes are: Dry; Slightly Wet; Moderately Wet; and Fully Wet.

Dry will be derived from the question on the 5-day Week Diary: "How was your day/night", and from the 2-day Episodic Weekend Diary if no leakages are reported during a diary day.

For each subject and visit the worst incontinence grade will be determined as the worst grading over the valid diary days preceding the study visit.

Improvement:

For Visit x (x=3, 4, 5, 6 and 7) the average over the valid week and weekend diary days will be calculated from the score of what was the worst leakage during the day", *i.e.*, 0 - Dry, 1 - Slightly Wet; 2 - Moderately Wet; and 3 - Fully Wet:

Worst Incontinence Grade at Visit x =

```
Sum of Worst Incontinence Gradings over the Valid Diary Days prior to Visit x
Number of Valid Diary Days
```

For each subject, improvement at Visit x if:

Worst Incontinence Grade (Visit x) - Worst Incontinence Grade (Visit 3 [Baseline]) < 0.

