7.2 List of Changes in SAP Version 3.0 from Version 2.0

The changes from the approved SAP Version 2.0 (dated 24-Sep-2021) to Version 3.0 that impact analyses are listed with the rationale in the table below.

SAP	Description	Rationale			
Section					
2.1	Secondary efficacy variable "Mean number of nighttime incontinence episodes per 24 hours" was deleted	Endpoint will no longer be analyzed due to changes in inclusion and exclusion criteria			
	Exploratory Endpoints. The following exploratory endpoints are added:	To be in line with previous studies			
	 Mean number of micturitions per 24 hours, adjusted for fluid intake: Number of micturitions per 24 hours that would be required at week 12/EoT to void the same total volume as voided at baseline 				
	 Difference in mean number of micturitions per 24 hours adjusted for fluid intake compared to the expected mean number 				
	• Mean volume voided per micturition as a percentage of expected bladder capacity				
	• Categorized mean volume voided per micturition as a percentage of expected bladder capacity (results and changes from baseline).				
	Added exploratory endpoint: "Change from baseline at the end of the 12-week treatment period (adolescents only) in Maximum Volume Voided"	To correct an omission. In previous version this end-point was only mentioned for children.			
4.5.1	Eligibility Deviations: Inclusion criterion 16 has been removed	Not part of ICCS criteria; unduly restrictive for enrollment			
	Exclusion criterion 1 has been removed	Not part of ICCS criteria; unduly restrictive for enrollment			
	Exclusion criteria 3 and 27 have been removed	No reason to exclude these subjects as monosymptomatic enuresis is known to co-occur with OAB			
5.4.2.3	For calculations reference is made to Center for Disease Control and Prevention website	Using validated SAS® code			
5.2.1	Derivation of mean volume voided was corrected.	Derivation was not correct			
Table cont	ple continued next page				

SAP	Description	Rationale	
Section			
5.2.5	Text in paragraph was updated	For clarification	
5.4.1	An AE designated as serious by either	Sentence was added for further clarification	
	the investigator or determined by	regarding the process.	
	Important Medical Event process will		
	be summarized as an SAE.		
	This paragraph was added with		
	"However, if the event is on IME list		
	but medical monitor agrees with		
	investigator that event is not SAE, then		
	event can be downgraded."		

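### SAP 5.3.1: adding 0.5 to a zero baseline makes a subject dry at both time points a complete responder on the literal text, or a non-responder if 0.5 enters only the denominator; neither category is meaningful

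*SAP*

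**What the plan says.** SAP 5.3.1 computes "the percent change from baseline to a Visit x (x=4, 5, 6 and 7) in the number of daytime incontinence episodes" as the visit count minus the baseline count, divided by the baseline count. Each count is a sum over the 7-day diary period. For a zero baseline it adds: "If the number of daytime incontinence episodes at baseline is equal to zero, a constant equal to 0.5 will be added to the baseline number". The stated purpose follows in the same sentence, where the constant is "added to the baseline number of leakages to allow denominator calculation".

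The categories are then fixed by R. "Complete responder will be defined as a subject with a 100% improvement from baseline", that is, R = -100%. A partial responder has R above -100% and up to -50%. "Non-responder will be defined as a subject with an improvement from baseline <50% or a worsening from baseline", that is, R > -50%.

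On whether a zero baseline can occur, protocol 5.1 (version 2.0), inclusion criterion 16, requires an average of at least one daytime incontinence episode per day in the baseline week. SAP 7.2 records, under section 4.5.1, "Eligibility Deviations: Inclusion criterion 16 has been removed". The reasons given are that the criterion is not an ICCS criterion and restricts enrolment too much. The same table attributes the deletion of the nighttime incontinence endpoint to changed entry criteria.

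On the neighbouring endpoint, SAP 5.3.2 states "For each subject and visit the worst incontinence grade will be determined as the worst grading over the valid diary days preceding the study visit". Under its improvement subheading it then says that "the average over the valid week and weekend diary days will be calculated", with Dry scored 0, and calls improvement any change below zero.

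**The concern.** A subject with no daytime leakage at baseline cannot show a reduction. A rule that still assigns a response category decides by convention, and here the wording allows two conventions that put the same unchanged subject at opposite ends of the scale. No worked example in the SAP settles which applies.

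At stake is the reported percentage of complete responders. On the literal text, subjects with nothing to respond to enter the top category in both arms. That raises both rates and narrows the gap between them. The endpoint also covers adolescents, planned at about 16 per arm (SAP 3), where one misplaced subject moves a rate by 1/16, about 6 percentage points.

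**Working it through.** The documents give no figure to reproduce for this endpoint, so the check applies the written rules directly.

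**Responder rule.** Let b be the baseline count and v the visit count, with R = (v - b)/b × 100%.

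| b | v | 0.5 in both terms | 0.5 in denominator only |
|---|---|---|---|
| 0 | 0 | (0 - 0.5)/0.5 = -100%, complete | (0 - 0)/0.5 = 0%, non-responder |
| 0 | 1 | (1 - 0.5)/0.5 = +100%, non-responder | (1 - 0)/0.5 = +200%, non-responder |
| 7 | 0 | -100%, complete | same |
| 7 | 3 | -57.1%, partial | same |
| 7 | 4 | -42.9%, non-responder | same |

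In these cases the reading changes the category only for the subject who is dry at both time points. Non-zero baselines are not touched by the constant.

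**Effect on the reported rates.** The share of zero-baseline subjects is not in the documents, so these inputs are assumptions: complete response of 30% (mirabegron) and 20% (placebo) among subjects wet at baseline, and a share q of each arm dry at both time points. The literal rule reports q + (1 - q) × rate. The denominator-only rule reports (1 - q) × rate.

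| q | Literal rule | Denominator only | Difference, either reading |
|---|---|---|---|
| 0 | 30% vs 20% | 30% vs 20% | 10 points |
| 5% | 33.5% vs 24% | 28.5% vs 19% | 9.5 points |
| 10% | 37% vs 28% | 27% vs 18% | 9 points |
| 20% | 44% vs 36% | 24% vs 16% | 8 points |

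Both readings shrink the difference by the same factor, 1 - q. Clarifying where 0.5 goes would settle the level of the rates but not the dilution. Restricting to subjects wet at baseline restores the 10 points.

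**Worst grading (minor).** A subject going from seven slightly wet days (grade 1) to six dry days and one fully wet day (grade 3) moves from 1 to 3 on the maximum and from 7/7 = 1.00 to 3/7 = 0.43 on the average. The shared label therefore covers two quantities that can move in opposite directions. The 0.43 counts all seven days. SAP 5 treats a weekend day as valid for incontinence only if a leakage is recorded, which would make it 3/6 = 0.50 or 3/5 = 0.60; the direction is the same.

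SAP 6.4.3 lists only scores 1 to 3. If dry days were left out of the average, a subject going from one fully wet and six slightly wet days (9/7 = 1.29) to one fully wet and six dry days would average 3/1 = 3.00 and appear worse. With Dry = 0 the visit average is 3/7 = 0.43, an improvement.

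**The case against.** The strongest case against has three parts.

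First, the stated purpose of the constant points to the denominator, and on that reading no subject is falsely called a complete responder. This stands in part. It shows that the literal result is not the only possible one. It does not rescue the rule, because the unchanged subject then becomes a non-responder and the dilution is identical.

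Second, an eligible subject under protocol version 2.0 cannot have a zero baseline, and protocol sections 5 and 10.3 prohibit waivers. A divide-by-zero rule may be routine safeguarding. The SAP mentions protocol version 3 only as applicable if it exists (sections 5.4.2.1 and 5.4.6). This stands as a limit: whether the rule is used depends on entry criteria not in the documents supplied. Still, SAP 7.2 speaks of changed entry criteria, SAP 4.5.1 now names only inclusion criteria 2 and 15 as automatic per-protocol exclusions, and the FAS (SAP 4.3) has no leakage requirement. The case needs a sound rule.

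Third, both endpoints are exploratory and only summarized. That is correct and limits the importance of the point.

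A reader might also infer that SAP 5.3.2 contains two competing improvement rules. The text does not support that. The only calculation under the improvement subheading is the average, and SAP 6.4.3 repeats it. The maximum appears in the preceding sentence with no improvement test attached, so this is a reused label.

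**Conclusion.** The zero-baseline rule in SAP 5.3.1 is defective for subjects who are dry by day at baseline and remain so. It calls them complete responders on the literal text and non-responders on the alternative reading, and neither describes them. It also sits oddly beside 5.3.2, where a subject fully dry at both time points has a change of 0 - 0 = 0 and is not improved.

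The size is unknown. In the illustration, a 10-point difference becomes 9.5, 9 or 8 points. That rests on assumed response rates and assumed shares, equal in the two arms, with every zero-baseline subject staying dry.

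A reader might infer that the full share of such subjects is added to each rate. That holds only against counting them all as non-responders. Against leaving them out, the literal rule adds 3.5, 7 or 14 points to the 30% arm (33.5 - 30, 37 - 30, 44 - 30) and 4, 8 or 16 points to the 20% arm.

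The secondary incontinence endpoints, daytime episodes and dry days, do not use the constant. The primary and secondary analyses, the significance level and the sample size are unaffected.

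**What to change.** In SAP 5.3.1, delete the 0.5 rule. Restrict the responder percentages to subjects with at least one daytime incontinence episode in the baseline diary. Report zero-baseline subjects separately by arm, as stayed dry or became wet. The cost is SAP wording and a somewhat smaller responder denominator.

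As minor wording repairs, delete or rename the maximum sentence in SAP 5.3.2 so that one label means one quantity, and add 0 = Dry to the scoring in SAP 6.4.3 so that it matches 5.3.2.

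All of this should be settled before unblinding, so that no reading is chosen with the results in view.
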